21.1.3 Suspected Adverse Reaction and Causality

Suspected adverse reaction is any adverse event for which there is a reasonable possibility that the drug caused the event. “Reasonable possibility” means there is evidence to suggest a causal relationship between the drugs/per protocol drug and adverse event.

The Investigator will use the following question when assessing causality of an adverse event to study drug: Is there a reasonable possibility that the drug caused the event? An affirmative answer designates the event as a suspected adverse reaction.

21.1.4 Relationship of Adverse Events and Serious Adverse Events to Study Drug

AEs that occur during clinical studies can be significant enough to lead to changes in the drug development program (e.g., changes in dose, changes in study population, or changes in the information given to subjects in the informed consent form.) Such changes are particularly possible with AEs that are suspected to be related to the study drug and with AEs that, in their most severe form, are life-threatening. It is therefore very important for the Investigator to give an opinion on the cause-effect relationship between an AE and the study drug.

Causality must be assessed when reporting the AE in the AE CRF and SAE forms. Only AEs judged by the Investigator, by the Sponsor, or by the Sponsor’s legal representative as having a reasonable, suspected, causal relationship to the study drug will be considered to be suspected adverse drug reactions. In general, the expression “reasonable, causal relationship” means that there is evidence or arguments to suggest a causal relationship.

21.1.5 Event Expectation

Unexpected: An event is considered “unexpected” when its nature (specificity) or severity is not consistent with the list of potential adverse reactions included in the current Investigator’s brochure.

Expected: An event is considered “expected” when its nature and severity are consistent with the list of potential adverse reactions included in the current IB.

21.1.6 **Recording of Adverse Events**

At each contact with the subject the study Investigator or his/her designee will seek information on AEs by specific questioning and examination. Information on all AEs will be immediately recorded in the source document and the data will be transferred to the CRF. All clearly related signs, symptoms and abnormal results will be recorded in the source document. The CRF will include a description, onset and resolution date, duration, maximum severity, assessment of causality, other suspected agent, subject's preexisting disease, action taken and outcome.

All AEs occurring during the study and long-term follow up period will be recorded and graded as described in [Section 21.1.7](#). The clinical course of each event will be followed until resolution, stabilization or until it has been reported as non-related to the investigational product.

21.1.7 **Toxicity Grading**

The AEs will be graded using NCI's CTCAE.

The list of potential ocular toxicities and their grading is shown in [Table 6](#). This list is a modification of the Ocular/Visual Adverse events v.3.0 (CTCAE), considering the specific subject population and the circumstances of the intervention.

The following AEs are defined as ocular toxicity and are to be assessed for grading as follows:

Table 6. Ocular toxicity scale

Toxicity	Grade 1	Grade 2	Grade 3 SAE	Grade 4 SAE
Keratitis (corneal inflammation/cornea ulceration)	Abnormal ophthalmologic changes only; intervention not indicated	Symptomatic; Medical intervention indicated	Symptomatic; Surgical intervention indicated	Perforation or blindness (worse than baseline visual function)
Glaucoma	Elevated intraocular pressure (EIOP) warranting topical agent for intervention	EIOP requiring topical agents and oral agents for intervention	EIOP requires operative intervention	Uncontrolled EIOP, resulting in blindness (worse than baseline visual function)
Cataract	Mild change from baseline, detected on ophthalmologic examination, not warranting intervention	Moderate change from baseline, detected on ophthalmologic examination, not warranting intervention	Severe change from baseline, detected on ophthalmologic examination, not warranting intervention NOT SAE	Severe change warranting operative intervention NOT SAE
Uveitis	Mild anterior uveitis, not warranting intervention	Moderate anterior uveitis, warranting intervention	Severe posterior or pan-uveitis, warranting medical intervention	Severe uveitis warranting operative intervention and threatening ocular integrity
Vitreous hemorrhage	Mild hemorrhage detected on ophthalmologic examination, not warranting intervention	Moderate hemorrhage not warranting intervention	Severe hemorrhage warranting vitrectomy	Uncontrolled vitreous hemorrhage, threatening ocular integrity
Retinal detachments/PVR (Proliferative vitreoretinopathy)	Localized, peripheral intervention not indicated	Not resolving; intervention not indicated	Operative intervention indicated	Operative failure, threatening ocular integrity

Systemic toxicity will be graded based on the scale, shown in [Table 7](#).

The following AEs are defined as systemic toxicity and are to be assessed for grading as follows:

Table 7. Systemic toxicity scale

Grade	Definition
1	Mild toxicity, usually transient, requiring no special treatment and generally not interfering with daily activities.
2	Moderate toxicity which may be ameliorated by simple therapeutic maneuvers, and impairs usual activities
3 SAE	Severe toxicity which requires therapeutic intervention and interrupts usual activities. Hospitalization may or may not be required.
4 SAE	Life-threatening toxicity which requires hospitalization

21.1.8 Severity Grading

The severity assessment is determined by the Investigator and is based on the definitions below. The maximum severity observed is to be recorded.

- 21.1.8.1 MILD: Subject is aware of event or symptom but event/symptom is easily tolerated.
- 21.1.8.2 MODERATE: Subject experiences sufficient discomfort to interfere with or reduce his or her usual level of activity.
- 21.1.8.3 SEVERE: Significant impairment of functioning; subject is unable to carry out usual activities and/or the subject's life is at risk from the adverse event.

21.2 DEVICE SAFETY

[REDACTED]

These potential events will be collected and reported to be consistent with 21CFR803, which notes that a user facility must report device related serious injury to the manufacturer.

The AEs that are attributed to device will be graded using a modification of NCI CTCAE (see [Table 5](#)). This list is a modification of the Ocular/Visual Adverse events v.3.0 (CTCAE), considering the specific subject population and the circumstances of the intervention.

The list of AESI is shown in [Table 8](#).

21.2.1 Device Adverse Events of Special Interest

When present at the time of surgery the following AESI may be assessed for grading as follows:

- 21.2.1.1 MILD: Subject is aware of event or symptom but event/symptom is easily tolerated.
- 21.2.1.2 MODERATE: Subject experiences sufficient discomfort to interfere with or reduce his or her usual level of activity.
- 21.2.1.3 MODERATELY SEVERE: Subject experiences impairment (e.g. vision loss up to 3 lines) or a related event that may require an additional procedure
- 21.2.1.4 SEVERE: Significant impairment of functioning; subject is unable to carry out usual activities and/or the subject's life is at risk from the adverse event.

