21.2.2 Device Adverse Events of Special Interest

Table 8. Device Adverse Events of Special Interest

Grade	1	2	3	4
Event	Mild	Moderate	Moderately Severe	Severe/significant

 • Endophthalmitis 	any occurrence resolving no change in vision	any occurrence not resolving vision loss up to 2 lines ETDRS	any occurrence not resolving vision loss up to 3 lines ETDRS	Panophthalmitis Or significant >3 lines vision loss ETDRS

 • Retinal detachment 	Localized, peripheral, intervention not planned	Not resolving, intervention not indicated	Operative indication indicated	Operative failure, threatening ocular integrity

 • Choroidal hemorrhage* 	Localized subretinal/subRPE hemorrhage	Not resolving, localized subretinal/subRPE hemorrhage	Operative indication indicated diffuse subretinal/sub RPE hemorrhage	Choroidal effusion, Choroidal rupture, Expulsive choroidal hemorrhage, and Unspecified choroidal hemorrhage

 • Perforation of retina 			Yes, any occurrence Operative indication indicated	Yes, any occurrence Operative failure

Grade	1	2	3	4
Event	Mild	Moderate	Moderately Severe	Severe/significant
• Cell egress			Yes, any occurrence Operative indication indicated	Yes, any occurrence Operative failure Significantly decreased vision
• Failure to deliver cells	•	•	Yes, any occurrence Operative indication indicated	Yes, any occurrence Operative failure Significantly decreased vision
• Unplanned vitrectomy	•	•	Yes, any occurrence	Yes, any occurrence Operative failure Significantly decreased vision

*Significant choroidal hemorrhage includes the following medical codes: choroidal effusion, choroidal rupture, expulsive choroidal hemorrhage, and unspecified choroidal hemorrhage

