21.3 SAFETY EXPEDITED REPORTING

21.3.1 Reporting to the IRB/IEC

All serious and unexpected AEs including grade 3-4 toxicities based on Table 6, Table 7 and Table 8 will be reported to the IRB and to the FDA and other relevant regulatory authorities.

It is the responsibility of the study Investigator or his/her designee to comply with applicable local regulatory requirements for the reporting of SAEs to the IRB/IEC. Investigators should immediately forward to the IRB/IEC any written safety report or update provided by the Sponsor in accordance with local regulatory requirements (e.g., safety report, IB, safety amendments, and updates).

A special SAE report will be created for this purpose and will include the following information:

- Subject number
- Description of the event
- Date of onset
- Current status
- Whether study treatment was discontinued
- The reason why the event was classified as serious
- Investigator's assessment of causality

All SAEs must be reported to the Sponsor as soon as possible and no later than 24 hours after study Investigator or his/her designee has knowledge of the event.

When an SAE occurs, the Investigator must do the following:

- Note in the subject's medical file the date on which the Investigator or site staff first learned of the event by any route (e.g., at a follow-up visit with the subject, by telephone with the subject, or from a third party).
- Immediately complete an AE CRF and an SAE form, without waiting for the clinical outcome or for the results of further investigation.
- Send to the assigned Medical Monitor (MM) de-identified copies of pertinent records, as soon as such copies are available, for example:
 - Hospital admission reports
 - Reports of further consultations
 - Laboratory test reports
 - Reports from other examinations aiding diagnosis
 - Results from pre-treatment assessments for comparison with the results obtained under treatment
 - Autopsy report, if an autopsy is performed
- Fulfill regulatory requirements for reporting to the IRB/IEC.

If an AE initially judged non-serious worsens and becomes serious, the Investigator must follow the procedure described above.

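### Protocol 21.2.1 makes device AESI grading optional and ties it to events present at surgery, in conflict with 21.2, Table 8 and 21.3.1, so delayed-onset events are left off the device scale or in doubt

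*Protocol*

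**What the plan says.** Protocol 21.2 (Device Safety) sets the general rule: "The AEs that are attributed to device will be graded using a modification of NCI CTCAE". It then refers to Table 8 for the AESI list. Some text at the start of 21.2 is redacted.

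Protocol 21.2.1 introduces a four-level severity scale with "When present at the time of surgery the following AESI may be assessed for grading as follows". The third level of that scale reads: "Subject experiences impairment (e.g. vision loss up to 3 lines) or a related event that may require an additional procedure".

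Protocol 21.2.2 gives Table 8, which carries no timing condition. Grade 2 endophthalmitis is "any occurrence not resolving vision loss up to 2 lines ETDRS"; Grade 2 retinal detachment is "Not resolving, intervention not indicated".

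Protocol 21.3.1 sends to the IRB and regulators "All serious and unexpected AEs including grade 3-4 toxicities based on Table 6, Table 7 and Table 8". Section 21.3.2, on reporting to the DSMB, names only Tables 6 and 7, as do the stopping rules in 10.2.

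For adverse events in general, 21.1.6 says "All AEs occurring during the study and long-term follow up period will be recorded and graded as described in" Section 21.1.7, which holds the CTCAE rule and Tables 6 and 7.

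**The concern.** The opening sentence of 21.2.1 does two things that the surrounding text does not. It uses permissive wording where 21.2 is mandatory, and it sets a time condition that 21.2, Table 8 and 21.3.1 do not show.

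The condition also fits badly with what is being graded. Whether an infection resolves, how many ETDRS lines are lost, and whether a hemorrhage persists are learned at later visits. The scale in 21.2.1 itself relies on the subject's awareness, discomfort in usual activity and lines of vision lost. These cannot be judged in an operation done under block, sedation or general anesthesia (11.3.2.4).

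Safety is the primary objective, and Cohort 4 uses two delivery systems. If sites read the sentence differently, the same delayed event could be a graded device AESI at one site and an ordinary AE at another. A comparison of the delivery systems would then partly reflect classification. The route to IRB and regulatory reporting through a Table 8 grade would also be uncertain for delayed events.

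**Working it through.** The protocol gives no figure to reproduce. The check is a comparison of the text.

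**Step 1: the four provisions side by side**

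| Provision | Mandatory? | Time condition visible? |
|---|---|---|
| 21.2, device-attributed AEs | Yes | None |
| 21.2.1, opening sentence | No, permissive | Present at surgery |
| 21.2.2, Table 8 | Not stated | None |
| 21.3.1, reporting of Table 8 Grade 3-4 | Yes | None |

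Only 21.2.1 differs.

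**Step 2: what Table 8 needs, and whether Table 6 covers the event**

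| Table 8 event | Criterion that needs follow-up | Own row in Table 6? |
|---|---|---|
| Endophthalmitis | Resolution; ETDRS lines lost | No |
| Retinal detachment | Failure to resolve | Yes |
| Choroidal hemorrhage | Failure to resolve | No |
| Perforation of retina | None necessarily (need for, or failure of, operation) | No |
| Cell egress | Significant loss of vision (Grade 4) | No |
| Failure to deliver cells | Significant loss of vision (Grade 4) | No |
| Unplanned vitrectomy | Significant loss of vision (Grade 4) | No |

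Six of the seven event types have at least one grade that needs follow-up. The rows of Table 6 are keratitis, glaucoma, cataract, uveitis, vitreous hemorrhage and detachment/PVR.

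**Step 3: which events can start after surgery.** Perforation, failed delivery and unplanned vitrectomy are essentially intra-operative, so the condition costs little there. Endophthalmitis, detachment, choroidal hemorrhage and cell egress can start later. For cell egress the protocol says so itself: 6.6.1 warns that cells may escape through the retinotomy until it heals. Detachment is covered by Table 6, which leaves endophthalmitis, choroidal hemorrhage and cell egress.

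**Step 4: illustrative size.** Inputs: about 12 eyes in Cohort 4 and 24 in all (Protocol 8.1.1; SAP 4.0), and a hypothetical single delayed event. Intervals are Clopper-Pearson, two-sided 95%.

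- Event counted: 1/12 = 8.3%. Lower limit 1 − 0.975^(1/12) = 0.2%; the upper limit solves P(X ≤ 1 | 12, p) = 0.025, giving 38.5%.
- Event omitted: 0/12 = 0%. Upper limit 1 − 0.025^(1/12) = 26.5%.
- Over all eyes: 1/24 = 4.2 points per event.

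These figures show how much one classification weighs at this sample size. They do not predict that any event will be missed. Cohort 4 also pools two delivery systems, so 12 is not a per-device denominator.

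**The case against.** The strongest reply is that 21.2 governs. It requires device-attributed events to be graded, and neither Table 8 nor 21.3.1 repeats the time condition. On that view the sentence in 21.2.1 merely introduces a generic severity scale, or it says which events qualify while their grade is taken from the later course. Part of 21.2 is redacted, as are Table 5 and the device-risk text in 19.4, so an onset window may be stated there.

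Delayed events also do not vanish. Detachment is graded in Table 6 without a time limit and feeds the stopping rules. All AEs are graded through long-term follow-up, 21.1.8 records maximum severity, and serious unexpected AEs are reported whatever table applies. Section 21.3.4 names intraocular infection among the product-related events for a 15-day report to the FDA. A site might also place an endophthalmitis in the uveitis row of Table 6, though the protocol does not say so.

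Much of this stands. A reader might infer that device AESIs are graded only at surgery, that a delayed infection or detachment is never graded, that the reporting trigger never fires, or that the device safety rate is therefore wrong. The documents do not support that. The sentence is permissive and does not say only; 21.2 and 21.3.1 point the other way; and no device AESI rate appears among the visible endpoints or in the SAP table list.

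What the reply does not remove is the conflict. If presence at surgery decides which events qualify, delayed-onset events still fail to qualify. A window in the redacted text would still have to be reconciled with the visible sentence.

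**Conclusion.** The inconsistency holds. Section 21.2.1 makes optional, and ties to the time of surgery, a grading that 21.2 makes mandatory, that Table 8 bases largely on later outcomes, and that 21.3.1 uses for reporting. Followed literally, delayed-onset endophthalmitis, choroidal hemorrhage and cell egress are excluded from the device AESI scale or left unclear, and no other ocular table has a row for them. The Table 8 Grade 3-4 trigger may not fire for them.

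The consequence is limited to device classification and one reporting route. It rests on the visible text alone. No numerical bias can be claimed; the step of 8.3 points per event in Cohort 4 is illustrative. It is worth correcting because a single event carries that much weight at this size and the correction uses data already collected.

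**What to change.** Replace the opening sentence of 21.2.1 with: *Table 8 events attributed to the delivery device or implantation procedure will be graded whenever they occur, from the start of surgery to the end of follow-up, at the worst grade reached, with onset date relative to surgery recorded.*

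The attribution condition matters. Without it, an unrelated detachment or infection years later would count as a device AESI.

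Reconcile the new sentence with 21.2 and 21.3.1, including any window in the redacted text. Check the reference in 21.2 to Table 5 for the grading scale, since 19.2 describes Table 5 as the summary of risks. In the SAP, add a listing of device AESIs by delivery system, with intra-operative and delayed events shown separately; Section 11 has ocular and systemic toxicity tables but none for device AESIs.

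Cost: one protocol sentence, one SAP listing and some re-grading of recorded AEs, because SAP 4.0 describes all 24 eyes as already treated. The AESI count may rise. The change concerns classification and reporting. It does not add Table 8 to the stopping rules or to the DSMB trigger in 21.3.2, which remain separate matters.

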21.2.2 Device Adverse Events of Special Interest

Table 8. Device Adverse Events of Special Interest

Grade	1	2	3	4
Event	Mild	Moderate	Moderately Severe	Severe/significant

 • Endophthalmitis 	any occurrence resolving no change in vision	any occurrence not resolving vision loss up to 2 lines ETDRS	any occurrence not resolving vision loss up to 3 lines ETDRS	Panophthalmitis Or significant >3 lines vision loss ETDRS

 • Retinal detachment 	Localized, peripheral, intervention not planned	Not resolving, intervention not indicated	Operative indication indicated	Operative failure, threatening ocular integrity

 • Choroidal hemorrhage* 	Localized subretinal/subRPE hemorrhage	Not resolving, localized subretinal/subRPE hemorrhage	Operative indication indicated diffuse subretinal/sub RPE hemorrhage	Choroidal effusion, Choroidal rupture, Expulsive choroidal hemorrhage, and Unspecified choroidal hemorrhage

 • Perforation of retina 			Yes, any occurrence Operative indication indicated	Yes, any occurrence Operative failure

Grade	1	2	3	4
Event	Mild	Moderate	Moderately Severe	Severe/significant
• Cell egress			Yes, any occurrence Operative indication indicated	Yes, any occurrence Operative failure Significantly decreased vision
• Failure to deliver cells	•	•	Yes, any occurrence Operative indication indicated	Yes, any occurrence Operative failure Significantly decreased vision
• Unplanned vitrectomy	•	•	Yes, any occurrence	Yes, any occurrence Operative failure Significantly decreased vision

*Significant choroidal hemorrhage includes the following medical codes: choroidal effusion, choroidal rupture, expulsive choroidal hemorrhage, and unspecified choroidal hemorrhage

21.3 SAFETY EXPEDITED REPORTING

21.3.1 Reporting to the IRB/IEC

All serious and unexpected AEs including grade 3-4 toxicities based on Table 6, Table 7 and Table 8 will be reported to the IRB and to the FDA and other relevant regulatory authorities.

It is the responsibility of the study Investigator or his/her designee to comply with applicable local regulatory requirements for the reporting of SAEs to the IRB/IEC. Investigators should immediately forward to the IRB/IEC any written safety report or update provided by the Sponsor in accordance with local regulatory requirements (e.g., safety report, IB, safety amendments, and updates).

A special SAE report will be created for this purpose and will include the following information:

- Subject number
- Description of the event
- Date of onset
- Current status
- Whether study treatment was discontinued
- The reason why the event was classified as serious
- Investigator's assessment of causality

All SAEs must be reported to the Sponsor as soon as possible and no later than 24 hours after study Investigator or his/her designee has knowledge of the event.

When an SAE occurs, the Investigator must do the following:

- Note in the subject's medical file the date on which the Investigator or site staff first learned of the event by any route (e.g., at a follow-up visit with the subject, by telephone with the subject, or from a third party).
- Immediately complete an AE CRF and an SAE form, without waiting for the clinical outcome or for the results of further investigation.
- Send to the assigned Medical Monitor (MM) de-identified copies of pertinent records, as soon as such copies are available, for example:
 - Hospital admission reports
 - Reports of further consultations
 - Laboratory test reports
 - Reports from other examinations aiding diagnosis
 - Results from pre-treatment assessments for comparison with the results obtained under treatment
 - Autopsy report, if an autopsy is performed
- Fulfill regulatory requirements for reporting to the IRB/IEC.

If an AE initially judged non-serious worsens and becomes serious, the Investigator must follow the procedure described above.

21.3.2 Reporting to the DSMB

The reporting rule described in [Section 21.3.1](#) should be applied for reporting to the DSMB. All serious and unexpected AEs including grade 3-4 toxicities based on Table 6 and Table 7 above should be reported to the DSMB. The SAE report created for notification of the IRB and regulatory authorities should be sent to the DSMB members within 48 hours from the event.

